The study will be explained as in the consent form and if agreed, subjects will elect either to or not to participate in the study after all risks and benefits are explained. Data to be collected will consist of age gravida/para, gestational age, BMI, time of date of intervention, time date of delivery, mode of delivery, bishop score at admission, bishop score after 12 hrs. of intervention, time and date of rupture of membranes, vaginal delivery within 24 hrs., hospital length of stay, other intrapartum and obstetrical interventions, complications in labor and delivery including but not limited to infections, hemorrhage, fetal decelerations and subject satisfaction. Data will be abstracted from subjects medical records as well as from direct interview with the subject. We will also collect basic neonatal data including birth weight, Apgar scores, rate of admission to neonatal intensive care unit, infections, and other neonatal complications. If elected to participate consents will be obtained and stored in subject chart. A copy of the consent will be given to the subject. Subjects will be consented in either English or Spanish by research personnel familiar with the language. Randomization will be done at time of consents. The study's time frame inclusive will be from 2016 till 2018. Data will be analyzed as per intent to treat.

Sample Size Calculation

The sample size will be calculated for the non-inferiority test.

The significance level of the test is targeted at 0.025, one-sided.

The rate of overall vaginal delivery is 71% and 76% for Foley catheter and Dilapan-S® , respectively. Higher rates are better.

The non-inferiority margin is $\delta=10\%$. It is defined as the largest treatment difference of no clinical importance.

The treatment allocation ratio will be 1:1.

The power of the non-inferiority test to be achieved is 90%.

Based on the above assumptions, the sample size would be 182 evaluable subjects in either treatment group, i.e. 364 evaluable subjects in total. Assuming that 13% of patients will not qualify for the primary analysis set (due to protocol deviation or considered as drop-out of loss to follow up), 420 patients are to be enrolled into this study.

5. Sub-Study Procedures: Not applicable.

6. Criteria for Inclusion of Subjects:

- Pregnant woman scheduled for induction of labor
- Age between 18 and 45 years
- Understanding and capable to sign informed consent
- Singleton pregnancy
- Gestational age ≥ 37 ^{0/7}weeks

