Rate of vaginal deliveries within 24 hours, rate of vaginal deliveries within 36 hours, rate of spontaneous vaginal deliveries, rate of operative vaginal deliveries and rate of caesarean sections will be analysed using similar statistical methods as described above for the primary endpoint, except for the definition of the non-inferiority margin and for the non-inferiority test. The 95% 2-sided CIs will be calculated for the treatment differences.

Time to reach active stage of labour defined as ≥ 6 cm (mins) will be analysed using survival analysis methods. Detailed methodology including set-up of censored values will be described in the final SAP. Change in Bishop score from baseline will be summarised by treatment group.

All rates above, time to reach active stage of labour and Bishop score are related to the secondary objectives and simultaneously, they are supportive measurements related to the primary objective. Patient satisfaction associated with the device used for cervical ripening (Patient Satisfaction Survey, question No. 12) will be evaluated as a secondary objective. Counts and proportions in all categories will be presented by treatment group. The location shift in response categories between the two treatment groups will be calculated and tested at the $\alpha = 0.05$ level of significance, two-sided.

Exploratory Variables Analysis

Exploratory variables will be summarised by treatment group.

Safety Variables Analysis

Safety variables will be summarised by treatment group.

Procedure for Accounting for Missing Data

Study subjects with missing primary variable will be evaluable neither for the ITT nor for the PPS population.

Missing primary variable data is expected to be very rare. If not, a different procedure may be refined in the SAP (e.g. a conservative imputation technique or sensitivity analyses) with the knowledge of the clinical data.

Procedure for Protocol Deviations

All protocol deviations will be listed by treatment group. Study subjects with a major protocol deviation will be excluded from the PPS analysis which makes demonstration of lack of sensitivity to protocol deviations possible (robustness).

Procedures for Deviations from the Original Statistical Plan

The SAP will contain more detailed description of the statistical analysis. If a need to change procedures of the analysis arises, an appropriate SAP update will be made. Major changes will require a protocol amendment.

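### The only between-arm effect measure for patient satisfaction is a location shift with no named estimator or confidence interval; on a short, skewed scale it would often read 0 beside a significant test

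*Combined protocol and SAP*

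**What the plan says.** Patient satisfaction with the ripening device is covered in the combined protocol and SAP, section 14 (Biostatistics), under Secondary Variables Analysis.

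- **Endpoint.** It is a single survey item: "Patient Satisfaction Survey, question No. 12) will be evaluated as a secondary objective". The number, wording and coding of its answers are not given.
- **Description.** "Counts and proportions in all categories will be presented by treatment group".
- **Effect and test.** "The location shift in response categories between the two treatment groups will be calculated and tested", at the 0.05 "level of significance, two-sided". The estimator and the test are not named, and no confidence interval is mentioned.
- **Later detail.** A general statement says "The SAP will contain more detailed description of the statistical analysis". It is not specific to satisfaction.

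In the same subsection, the secondary delivery rates do get 95% two-sided confidence intervals for the treatment differences. Section 13 lists better satisfaction among the benefits that the trial may show.

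**The concern.** In its usual sense, a location shift is the Hodges-Lehmann estimate: the median of all differences between a woman in one arm and a woman in the other. It presumes that one distribution is the other moved along a continuous scale. The plan's own sentence refers to response categories. On integer-coded categories the estimate can only be a whole number, or a half at an exact tie. It stays at 0 until at least half of all pairs favour one arm outright.

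A rank test needs no such majority. It can therefore detect a real difference while the accompanying estimate reads 0. A secondary objective with a formal test would then be reported with an effect size that does not reflect what the test found, and with no interval around it.

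**Working it through.** **The plan's sample size.** The documents give no figure for satisfaction, so the planned evaluable number sets the size of the check. The plan says "The rate of overall vaginal delivery is 71% and 76% for Foley catheter and Dilapan-S", with a 10-point margin, one-sided 0.025 and 90% power. Per arm:

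n = [0.71×0.29 + 0.76×0.24] × (1.960 + 1.282)² / (0.05 + 0.10)² = 0.3883 × 10.51 / 0.0225 = 181.3, rounded up to 182.

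This agrees with "the sample size would be 182 evaluable subjects in either treatment group, i.e. 364 evaluable subjects in total". Enrolment: 364 / 0.87 = 418.4, so 419 against the stated 420.

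**Assumptions, none of them in the documents.** The number of categories, the Foley distribution, a proportional-odds treatment effect, the Hodges-Lehmann estimator on integer codes, and a tie-corrected Mann-Whitney test at two-sided 0.05.

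**One case by hand.** Take Foley answers of 5/10/20/35/30% from worst to best, and an odds ratio of 2.0. Dividing each cumulative odds by 2 gives Dilapan-S answers of 2.56/5.54/13.10/32.63/46.15%.

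- P(Dilapan-S better) = 0.0554×0.05 + 0.1310×0.15 + 0.3263×0.35 + 0.4615×0.70 = 0.460
- P(tie) = 0.0256×0.05 + 0.0554×0.10 + 0.1310×0.20 + 0.3263×0.35 + 0.4615×0.30 = 0.286
- P(Foley better) = 1 − 0.460 − 0.286 = 0.254

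Neither arm wins half of the pairs, so the median pairwise difference is 0. P(better) plus half the ties is 0.460 + 0.143 = 0.603, clearly above the no-difference value of 0.5.

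**Simulation, three distributions skewed to the favourable end** (5/10/20/35/30, 3/5/12/30/50 and 5/15/40/40%; 182 per arm, 2,000 trials each):

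- Odds ratio 1.75: the test is significant in about 78-83% of trials. Among those, the shift is exactly 0 in 96-100%.
- Odds ratio 2.0: the shift is exactly 0 in 88-100% of significant trials.
- Odds ratio 2.5: in the first distribution the share falls to about 64%.

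**Simulation, wider range of scales.** Share of significant trials with a shift of exactly 0:

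| Assumed Foley answers | OR 1.5 | OR 2 | OR 3 |
|---|---|---|---|
| 2 categories, 30/70 | 100% | 100% | 100% |
| 3, skewed (10/25/65) | 100% | 100% | 100% |
| 3, flat | 100% | 99% | 68% |
| 4, skewed (5/10/30/55) | 100% | 100% | 100% |
| 4, flat | 96% | 71% | 12% |
| 5, skewed (3/7/15/35/40) | 100% | 99% | 85% |
| 5, centred (10/20/40/20/10) | 98% | 72% | 6% |
| 5, flat | 79% | 37% | 2% |
| 7, flat | 26% | 7% | 0% |
| 11, skewed to the top | 93% | 77% | 30% |
| 11, flat | 0% | 0% | 0% |

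**Does the alternative move with the effect?** Yes. For the five skewed categories in the table, P(better) plus half the ties averages 0.558, 0.596 and 0.646 at odds ratios of 1.5, 2 and 3. Over the same effects the Hodges-Lehmann shift stays at 0 in 100%, 99% and 85% of significant trials.

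**The case against.** The strongest reply is that the estimator has been supplied by the reader. The plan does not name Hodges-Lehmann, and other readings fit its sentence. A difference in mean category scores would not stick at 0: in the hand-worked distribution it is about 0.32 categories at odds ratio 1.75 and 0.39 at 2.0. A proportional-odds model is itself a location shift on a latent scale, so one of the remedies below may already be what was meant. All of this stands, and it makes the point conditional. It does not remove it: an effect measure that can be read in three ways, on an item with a formal test, still has to be pinned down. The mean-score reading would also need equally spaced categories, which the plan does not state.

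A reader might infer that the estimate will almost always be 0. The documents do not support that. The scale of question No. 12 is not shown, and the table runs from 0% to 100%.

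A reader might also infer that the satisfaction result could not be interpreted. That goes too far: category counts and percentages by arm are planned, so direction and rough size will be visible. What they lack is a single effect size with an interval.

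Finally, detail is left to a later SAP. That could settle the estimator and add an interval. But the plan has already chosen the type of measure, and a promise of more detail does not change that choice.

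**Conclusion.** The point holds in conditional form. The plan gives satisfaction one between-arm effect measure and leaves its estimator, test and interval open. If the measure is the median pairwise difference and question No. 12 has a short scale with answers bunched at the favourable end, a significant test would often come with an estimate of exactly 0. The 88-100% figure for odds ratios of 1.75 to 2.0 rests on three assumed distributions of 4 or 5 categories, 182 women per arm and proportional odds. It should not be quoted without those conditions.

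The validity of the rank test is not in question. This is one secondary item, so the matter is a cheap improvement and not a threat to the trial's conclusions.

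**What to change.** In the SAP, before outcome data are reviewed by arm (the trial is open-label):

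1. State the categories of question No. 12, their order and their coding.
2. Replace the location shift with the probability that a Dilapan-S woman is more satisfied than a Foley woman, ties counted half, with a 95% confidence interval. A proportional-odds ratio with a 95% confidence interval is an acceptable alternative. Choose one in advance.
3. Name the test: tie-corrected Wilcoxon/Mann-Whitney at two-sided 0.05, which matches either measure.
4. Keep the planned category counts and percentages by arm.

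The cost is a sentence or two of SAP text. No new data are needed. The small downside is that the effect is no longer in units of categories; the retained counts cover that.
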